15.3.1.2. ANALYSIS

BILAG domain scores will be tabulated by treatment group at each visit, plus categories for grade B or worse and grade C grade or better. Shifts from baseline among the grades will be tabulated similarly. Individual grades for each domain will be graphed over time, treating grade as ordinal, with one plot per subject.

The analysis for BILAG clinical response (full and partial) will replicate that performed for SRI.

15.3.2. BICLA RESPONSE

15.3.2.1. DERIVATION

The BILAG-based Combined Lupus Assessment (BICLA) definition of response includes all of the following:

- BILAG-2004 improvement (all A scores at baseline improved to B/C/D, and all B scores improved to C or D);
- no worsening in disease activity (no new BILAG-2004 A scores and ≤ 1 new B score);
- no worsening of total SLEDAI-2K score from baseline (no change or reduction from baseline);
- no significant deterioration (< 10% worsening) in 100 mm visual analogue PhGA;
- no treatment failure (See Section 15.3.15)

Patients' BICLA response will be derived from the above criteria for visits on which all of the component variables are captured.

Document: SGN35-022 SAP v1 V0.3
Author: [REDACTED]

Version Number: 1.0
Version Date: 31Jan2017

Template No: CS_TP_BS016 – Revision 3
Effective Date: 01Apr2016

Reference: CS_WI_BS005

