### **4.4 Selection of Study Population**

#### **4.4.1 Inclusion Criteria**

Subjects may be entered in the study only if they meet all of the following criteria:

1. Subject is able to provide written, informed consent.

2. Subject is an adult, aged  $\geq 18$  years.
3. Women of childbearing potential or male subjects with a WOCBP partner, will use 2 forms of highly-effective contraception method during the study through 6 months following the last dose of study drug. Women of childbearing potential includes any female who has experienced menarche and who has not undergone successful surgical sterilization (hysterectomy, bilateral tubal ligation, or bilateral oophorectomy) or is not postmenopausal. Postmenopausal is defined as amenorrhea  $\geq 12$  consecutive months without another cause, or documented follicle-stimulating hormone level  $> 35$  mIU/mL for women with irregular menstrual periods and on hormone replacement therapy (HRT). Acceptable forms of effective contraception include: established use of oral, injected, or implanted hormonal methods of contraception; placement of an intrauterine device or intrauterine system; barrier methods of contraception (condom or occlusive cap) with spermicidal foam/gel/film/cream/suppository; male sterilization; and true abstinence. Women of childbearing potential taking concomitant mycophenolate and oral contraceptives must use a barrier method of contraception along with their oral contraceptives.
4. If subject is a WOCBP, a serum pregnancy test result at screening and urine pregnancy test result at baseline must be negative.
5. Subjects must have a documented diagnosis of SLE for at least 6 months prior to screening according to both of the following:
  - a. fulfills at least 4 of 11 of the 1997 Update of the 1982 American College of Rheumatology (ACR) Revised Criteria for Classification of SLE; and
  - b. has a history of positive ANA ( $\geq 1:80$ ) or anti-dsDNA ( $\geq 30$  IU/mL) test prior to screening.
6. Subjects must have a positive ANA ( $\geq 1:80$ ) or anti-dsDNA ( $\geq 30$  IU/mL) test at screening (a single rescreening of previously positive subjects who were negative at screening will be allowed).
7. Subjects must demonstrate active SLE as indicated by a SLEDAI score  $\geq 4$  points at screening and at baseline.

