15.3.1.1. DERIVATION

BILAG CLINICAL RESPONSE

BILAG Clinical Response is defined as:

- BILAG C scores or better in all organ domains; which includes by definition no new BILAG A or B scores in any organ domain

BILAG PARTIAL CLINICAL RESPONSE

BILAG Partial Clinical Response is defined as:

- at most 1 BILAG A or B score in any organ domain

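### BICLA and BILAG response can be met with no change from baseline, because entry requires no BILAG A or B score and the analyses keep subjects who have none

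*SAP*

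**What the plan says.** Entry. Protocol 4.4.1, criterion 7, reads "Subjects must demonstrate active SLE as indicated by a SLEDAI score" of at least 4 points at screening and at baseline. BILAG is assessed at both visits (Protocol 4.3.1 and 4.3.2.1), but no inclusion or exclusion criterion asks for a BILAG A or B.

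BICLA (SAP 15.3.2.1; Protocol 6.2.2 is essentially the same). The improvement component is "BILAG-2004 improvement (all A scores at baseline improved to B/C/D, and all B scores improved to C or D"). The SLEDAI component is "no worsening of total SLEDAI-2K score from baseline (no change or reduction from baseline"). For the rest, a subject may gain one B but not an A, the PhGA may rise by less than 10%, and treatment failure rules out a response. The SAP points to 15.3.15 for treatment failure, but that section is SF-36; the definition is in 15.3.13.

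BILAG response (SAP 15.3.1.1). Clinical response is "BILAG C scores or better in all organ domains; which includes by definition no new BILAG A or B scores in any organ domain". Partial response is "at most 1 BILAG A or B score in any organ domain". Protocol 6.2.3.3 also lists organ-specific response by domain score.

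Analysis. SAP 15.3.1.2 and 15.3.2.2 apply the SRI analysis to these endpoints: Fisher's exact tests of each dose against placebo, relative risks with confidence intervals, and logistic regression on dose (15.2.1.2). The set is the FAS (15.3), meaning all randomized subjects (5.2). The denominator is everyone in the set with data at the visit (15.1). No rule covers subjects without an A or B at baseline.

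**The concern.** A response endpoint should separate subjects who got better from those who did not. Here the improvement component of BICLA looks only at domains graded A or B at baseline. With no such domain it is satisfied automatically, and the remaining BILAG, SLEDAI and PhGA components are satisfied by standing still. BILAG clinical and partial response describe a state at the visit, so they can be true before the first dose.

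Nothing keeps these subjects out of the trial or out of the analysis. They add to the numerator and denominator in every group, raise all response rates and pull differences and relative risks toward no effect. The study's stated purpose is to inform a larger efficacy study (Protocol 8.1, SAP 3.1.1). An inflated placebo BICLA rate, or a diluted effect, would carry into that design.

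**Working it through.** The documents give no figure on this point, and the sample size rests on clinical judgment, so there is nothing to reproduce. The check has two parts.

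**1. Apply the definitions to subjects whose SLEDAI and PhGA do not change and who have no treatment failure.**

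| BILAG grades | BICLA | BILAG clinical | BILAG partial (SAP) | SRI |
|---|---|---|---|---|
| Only C/D/E, unchanged | met | met | met | not met |
| Only C/D/E, then one new B | met | not met | met | not met |
| One B, unchanged | not met | not met | met | not met |
| Two Bs, unchanged | not met | not met | not met | not met |

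The second row is a BICLA responder whose BILAG has worsened, because one new B is allowed. The third row shows that partial response is met at baseline even with an active domain. By the same reasoning, organ-specific response is met at baseline in any domain already graded C or better. SRI fails throughout because it needs a SLEDAI fall of at least 4 (SAP 15.2.1.1).

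**2. Illustrate the size for BICLA or BILAG clinical response.**

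Inputs from the documents: 8 subjects per dose and 8 on placebo in total (Protocol 4.1), with placebo pooled (Protocol 8.2, SAP 6.1).

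Assumed inputs, none of them in the documents: a share f of 10% to 30% with no A or B at baseline; 90% of these still counted as responders at the visit, equally in each group; true response among the rest of 25% on placebo and 50% on drug.

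- Observed rate = (1 − f) × true rate + f × 0.9
- Observed difference = (1 − f) × (0.50 − 0.25), because the f × 0.9 term cancels

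| f | Placebo | Drug | Difference | Relative risk |
|---|---|---|---|---|
| 0 | 25% | 50% | 25 points | 2.00 |
| 10% | 0.9 × 0.25 + 0.09 = 31.5% | 0.9 × 0.50 + 0.09 = 54% | 22.5 points | 0.54/0.315 = 1.71 |
| 30% | 0.7 × 0.25 + 0.27 = 44.5% | 0.7 × 0.50 + 0.27 = 62% | 17.5 points | 0.62/0.445 = 1.39 |

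Other assumed values give the same pattern. With 20% against 50%, and every such subject staying unchanged, the 30-point difference becomes 27, 24 and 21 points at shares of 10%, 20% and 30%.

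The chance that a group of 8 holds at least one such subject is 1 − (1 − f)^8: 57% at f = 10% and 94% at f = 30%. One subject in 8 is 12.5 percentage points.

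**The case against.** The best case against runs as follows.

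- **Low stakes.** These endpoints are exploratory, there is no multiplicity control (SAP 7.4), and the secondary endpoint is untouched. This stands and limits the weight of the point.
- **Swamped by noise.** With 8 against 8 at 25% and 50%, the approximate 95% half-width is 1.96 × √(0.1875/8 + 0.25/8) = 46 points, far more than a loss of 2.5 to 7.5 points. This also stands: no single comparison will turn on the dilution. But the inflation of the rates is systematic, and it is those rates that a later design would use.
- **A state is a legitimate summary.** The proportion with C or better in all domains is worth reporting. As a description that is fair. Labelling it response and testing it against placebo treats it as an effect.
- **Visible elsewhere.** SAP 15.3.1.2 tabulates domain grades and shifts from baseline, so affected subjects can be found. The rates and tests are still not corrected.
- **Few such subjects.** Protocol 2.5 describes moderate to severe disease, and criterion 8 requires failure of a prior therapy. Neither sets a BILAG grade, so the share could be small but is unknown.
- **Treatment failure filters some out.** This is true for BICLA: SAP 15.3.13 includes increased corticosteroids and withdrawal for adverse events or lack of efficacy. The assumed 90% may therefore be too high for BICLA, or may differ between groups. BILAG clinical and partial response have no such filter.

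A reader might infer that only 2 placebo subjects per cohort carry each comparison, so that chance imbalance dominates. The plan does not do that: placebo is pooled to about 8. Nor are the automatic responders untreated subjects. Most are randomized to drug, and stable background therapy is allowed in every group (Protocol 5.7.2).

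**Conclusion.** Wrong as written. Applied literally, the SAP counts unchanged subjects as BICLA, BILAG clinical and BILAG partial responders, and in one case counts a subject with a new B as a BICLA responder. That conclusion follows from the text and needs no assumption about numbers.

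The size is not known. On the assumed shares of 10% to 30%, with 90% persistence in each group, a 25-point difference shrinks to 22.5 to 17.5 points and the placebo rate rises from 25% to 31.5% to 44.5%. Unequal persistence between groups would change these figures.

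A reader might infer that the trial's main efficacy result is compromised. The documents do not support that: SRI cannot be met without a SLEDAI fall of at least 4. A reader might also suppose that requiring one A or B at baseline cures every endpoint. It does not cure partial response, which a subject with a single A or B already meets.

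**What to change.** Before database lock and unblinding, amend SAP 15.3.1 and 15.3.2 so that:

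- BICLA and BILAG clinical response are analysed in FAS subjects with at least one BILAG A or B at baseline;
- BILAG partial response is analysed in subjects who do not already meet it at baseline, which under the SAP definition means at least two domains graded A or B;
- organ-specific response is analysed in subjects with an A or B in that domain at baseline;
- the denominators are shown for each group, with the all-FAS version alongside;
- the change is recorded in SAP 3.4, which now reports no meaningful deviations from the protocol.

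No new data are needed. The restriction uses a predose, blinded assessment, so it does not select on outcome. SAP 7.5 rules out subgroup analyses, so the text should say that this defines who can show the response. SAP 15.3.19.2 already repeats analyses in a subset, subjects with active renal disease.

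The cost is smaller denominators for exploratory endpoints: at shares of 10% to 30%, an expected 8 × 0.9 = 7.2 to 8 × 0.7 = 5.6 per group for BICLA and BILAG clinical response, and no more than that for partial response.

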15.3.2.2. ANALYSIS

The analysis for BICLA response will replicate that performed for SRI.

15.3.3. CLASI

The Cutaneous Lupus Erythematosus Disease Area and Severity Index (CLASI) consists of measures of cutaneous disease activity and damage over 14 anatomical locations, with the scores ranging from 0-70 and 0-56, respectively, and higher scores indicating greater severity (Klein, 2010). Scores are determined by trained investigators and are recorded on the eCRF.

15.3.3.1. DERIVATIONS

CFB, PCFB, CFEOT and PCFEOT will be calculated for this endpoint.

15.3.3.2. ANALYSIS

Observed and change values will be summarized by treatment group. Means with 95% CI will be plotted for Observed and CFB values over time with treatment groups overlaid. Individual values over time will be plotted over time per treatment group.

An analysis of covariance model will be fit for CFB/CFEOT at each scheduled time, with a fixed effect for treatment group and a covariate for the baseline value. Comparisons will be made between each dose level, and all active treated subjects combined versus placebo at the 5% significance level (two-sided). Least-squares treatment means and mean differences will be estimated with 95% CI and two-sided p-values for the test of no treatment difference.

15.3.4. SLEDAI-2K

The Systemic Lupus Erythematosus Disease Activity Index 2000 (SLEDAI-2K) is numeric index based on 24 outcomes covering 9 organs systems, each with scores ranging from 1 to 8 when the outcome is present (Yee, 2011). The total SLEDAI-2K score is the simple sum of the scores and falls between 0 and 105, with higher scores representing higher disease activity. Scores are determined by trained investigators and are recorded on the eCRF.

15.3.4.1. DERIVATIONS

CFB, PCFB, CFEOT and PCFEOT will be calculated for this endpoint and the organ systems.

A SLEDAI clinical response is defined as an improvement (reduction) of 4 or more points, relative to baseline.

15.3.4.2. ANALYSIS

The analyses for SLEDAI-2K scores will replicate those performed for CLASI.

The analysis for SLEDAI clinical response will replicate those performed for SRI.

Boxplots profiles of SLEDAI-2K through time (study day) for each dose level. Stacked bar graphs will be generated for each subject with all visits included, with stacks comprised of the scoring domains, and dose levels comprising separate pages.

15.3.5. GLOBAL ASSESSMENTS: PtGP, PtGA, PhGA

Physician's Global Assessment of Disease Activity (PhGA), Patient's Global Assessment of Disease Activity (PtGA), Patient's Global Assessment of Pain (PtGP) are assessed as visual analog scale responses ranging from 0 to 100 mm, with higher numbers indicating greater activity/pain.

15.3.5.1. DERIVATIONS

CFB, PCFB, CFEOT and PCFEOT will be calculated for these endpoints. The following reductions in global scores will be derived: 20%, 50% and 70%, labeled as PhGA20/50/70, PtGA20/50/70, PtGP20/50/70.

15.3.5.2. ANALYSIS

The analyses for global assessments will replicate those performed for CLASI. PhGA20/50/70, PtGA20/50/70, and PtGP20/50/70 will be tabulated by treatment.

Grouped subject-level line (spaghetti) plots vs study day will be generated, with one plot per dose level.

15.3.6. SWOLLEN AND TENDER JOINT COUNTS

Swollen and tender joint counts (SJC; TJC) are measured out a total of 66 and 68 joints, respectively.

15.3.6.1. DERIVATIONS

CFB, PCFB, CFEOT and PCFEOT will be calculated for both joint counts. The following reductions in PCFB joint counts from baseline will be derived: 20%, 50% and 70% (SJC20/50/70 and TJC20/50/70).

15.3.6.2. ANALYSIS

The analyses for SJC/TJC will replicate those performed for CLASI. SJC20/50/70 and TJC20/50/70 will be summarized by treatment.

15.3.7. ACR RESPONSE

The American College of Rheumatology (ACR) response criteria are standard criteria used to identify improvement across 7 biometrics by a specified minimum percentages of 20, 50 and 70%.

15.3.7.1. DERIVATIONS

ACR20, ACR50 and ACR70 responses relative to baseline will be assessed on Days 43, 85 and 127 using the standard definition (Felson, 1995), namely a 20/50/70% reduction in both SJC and TJC, plus a 20/50/70% reduction in 3 of the following 5 tests: PtGP, PtGA, PhGA, HAQ-DI and ESR. Response will only be assessed for subjects for whom sufficient variables are available at the given visit, and will otherwise be regarded as a missing value.

15.3.7.2. ANALYSIS

The analysis for ACR response will replicate that performed for SRI.

15.3.8. SELENA SLE FLARES

Occurrence of SELENA SLE flares will be recorded on the eCRF.

A mild/moderate flare is defined to include any of the following:

- increase in SLEDAI \geq 3 points, relative to baseline
- new/worse skin, stomatitis, serositis, arthritis, or fever
- increased prednisone < 0.5 mg/kg/day
- added NSAID/hydroxychloroquine
- increase in PhGA ≥ 1.0 , relative to baseline

A severe flare is defined to include any of the following:

- increase in SLEDAI ≥ 12 points, relative to baseline
- new/worse CNS-SLE, vasculitis, nephritis, myositis, platelet count $< 60,000/\mu\text{L}$, hemolytic anemia with hemoglobin < 7 mg/dL, requiring doubling > 0.5 mg/kg/day prednisone
- hospitalization for SLE
- prednisone > 0.5 mg/kg/day
- new immunosuppressive increase in PhGA to > 2.5 , relative to baseline

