8. Subject has failed (defined as inadequate response, such as worsening or continued disease activity while on treatment) at least one of the following treatments for SLE after a trial of at least 3 months:

- a. mycophenolate mofetil or mycophenolic acid, azathioprine, methotrexate, leflunomide, 6-mercaptopurine, calcineurin inhibitors, cyclophosphamide;
- b. belimumab, other B cell activating factor (BAFF) pathway antagonists, or abatacept; or
- c. antimalarials, such as hydroxychloroquine, in combination with prednisone of at least 10 mg/day or equivalent.

9. If taking the following medications, the subject must be on a stable dose prior to the baseline visit for at least the durations indicated and be willing and able to continue at stable doses throughout the study, unless otherwise allowed by this protocol:

- a. corticosteroids (up to 40 mg/day prednisone or equivalent): 4 weeks;
- b. hydroxychloroquine or other antimalarials: 3 months;
- c. mycophenolate mofetil or mycophenolic acid, azathioprine, methotrexate, leflunomide, or 6-mercaptopurine: 3 months; or
- d. nonsteroidal anti-inflammatory drugs (NSAIDS) or COX-2 inhibitors at or below the maximum approved dose: 2 weeks.

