### **5.7.2      Allowed Medications**

If taking the following medications, the subject must be on a stable dose prior to the baseline visit for at least the durations indicated and be willing and able to continue at stable doses throughout the study:

- corticosteroids (up to 40 mg/day prednisone or equivalent): 4 weeks;
- hydroxychloroquine or other antimalarials: 3 months;
- mycophenolate mofetil, mycophenolic acid, azathioprine, methotrexate, leflunomide, or 6-mercaptopurine: 3 months;
- NSAIDS and COX-2 inhibitors at or below the maximum approved dose: 2 weeks; or
- Oral, injected, or implanted hormonal methods of contraception, as well as HRT: 3 months.

Temporary increases in corticosteroid dosage (“bursts”) are permissible during the study as follows.

- The maximum duration of a burst is limited to 14 days duration on no more than 2 occasions.
- The corticosteroid dose must return to the preburst dose or lower at least 1 week before the 12-week assessments.
- The maximum dosage during a burst is up to 0.5 mg/kg prednisone, or equivalent, including any other steroids being given.

- The specific dose and taper schedule is at the discretion of the Investigator.

No increases in corticosteroid dosage outside of bursts are permitted. Decreases in the maintenance corticosteroid dose are allowed.

MMAE is primarily metabolized by cytochrome P450 enzyme 3A4 (CYP3A4), and is a substrate of P-glycoprotein (P-gp). Caution should be used in co-administering drugs which strongly inhibit CYP3A4 or P-gp, since increased MMAE exposures may result.

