## 6.2.2 Response Definitions

The following definitions will be used to evaluate the response assessments.

- **BILAG Clinical Response** is defined as (must meet both criteria):
  - BILAG C scores or better in all organ domains; and
  - no new BILAG A or B scores in any organ domain.
- **Systemic Lupus Erythematosus Responder Index (SRI)** definition of response includes:
  - reduction in Safety of Estrogens in Lupus Erythematosus National Assessment (SELENA)-SLEDAI of at least 4 points;
  - no new BILAG A organ domain scores and no more than 1 new BILAG B score; and
  - no worsening (increase of < 0.3) in PhGA versus baseline.
- **BILAG-based Combined Lupus Assessment (BICLA)** definition of response includes:
  - BILAG-2004 improvement (all A scores at baseline improved to B/C/D, and all B scores improved to C or D);
  - no worsening in disease activity (no new BILAG-2004 A scores and  $\leq$  1 new B score);
  - no worsening of total SLEDAI-2K score from baseline;
  - no significant deterioration (< 10% worsening) in 100 mm visual analogue PhGA; and
  - no treatment failure (defined as nonprotocol treatment [ie, new or increased immunosuppressives or antimalarials or increased or parenteral corticosteroids] or premature discontinuation from study treatment).
- **Active renal disease** is defined as either:
  - both of urinary protein:creatinine ratio  $\geq$  0.5 and active urinary sediment as defined by at least one of the following (in the absence of urinary tract infection):
    - more than 5 red blood cells (RBCs)/high power field (hpf) (or above the reference range for the laboratory),

- more than 5 white blood cells (WBCs)/hpf (or above the reference range for the laboratory), or
- presence of cellular casts (RBC or WBC); or
- isolated severe proteinuria without active sediment (eg,  $\geq 3.5$  grams/day or equivalent).
- **SELENA SLE flare** definitions include:
  - SELENA mild/moderate flare:
    - a change in SLEDAI  $\geq 3$  points,
    - new/worse skin, stomatitis, serositis, arthritis, or fever,
    - increased prednisone  $< 0.5$  mg/kg/day,
    - added NSAID/hydroxychloroquine, or
    - $\geq 1.0$  increase in PhGA (on a 0 to 3 scale);
  - SELENA severe flare:
    - change in SLEDAI  $> 12$ ,
    - new/worse CNS-SLE, vasculitis, nephritis, myositis, platelet count  $< 60,000/\mu\text{L}$ , hemolytic anemia with hemoglobin  $< 7$  mg/dL, requiring doubling or  $> 0.5$  mg/kg/day prednisone,
    - hospitalization for SLE,

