15.3.13. TREATMENT FAILURE

Treatment failure is defined as meeting at least one of the following criteria, and will be recorded on the eCRF:

- Death
- Premature withdrawal from the study due to adverse events or lack of efficacy
- Addition of new or increased immunosuppressive or antimalarial or increased or parenteral corticosteroids.

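### The prednisone item for a severe SELENA flare is an absolute dose, so a permitted and unchanged background dose can meet it

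*SAP*

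**What the plan says.** SAP 15.3.8 introduces the list with "A severe flare is defined to include any of the following". One bullet, standing alone, is "prednisone > 0.5 mg/kg/day". Protocol 6.2.2 has the same bullet under "SELENA severe flare". Neither document adds a reference dose or a change word.

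The neighboring rules are worded differently:

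- The mild/moderate flare item is "increased prednisone < 0.5 mg/kg/day".
- The organ-specific severe item names a prednisone level only as something that new or worse disease requires.
- The SAP states its SLEDAI and PhGA flare items relative to baseline.
- Treatment failure in SAP 15.3.13 includes "Addition of new or increased immunosuppressive or antimalarial or increased or parenteral corticosteroids".

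On background steroids, inclusion criterion 9a (protocol 4.4.1) allows "corticosteroids (up to 40 mg/day prednisone or equivalent): 4 weeks", to be continued at a stable dose on study. Protocol 5.7.2 allows up to two short bursts, capped at 0.5 mg/kg in total. It bars any other increase and adds: "Decreases in the maintenance corticosteroid dose are allowed". The eligibility criteria set no weight limit and no mg/kg cap on the background dose.

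On data capture, SAP 15.3.8 says: "Occurrence of SELENA SLE flares will be recorded on the eCRF". SAP 15.3.8.1 derives only the time to flare. SAP 15.3.8.2 analyzes incidence by severity and overall, as for SRI, and estimates flare-free survival by Kaplan-Meier.

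**The concern.** A flare is meant to be something that happens after randomization. A bare dose level does not describe an event: a subject can be above it on Day 1 and stay there at every visit without any worsening. The other steroid rules, and the SAP's SLEDAI and PhGA flare items, all carry a reference point, so its absence here looks like an oversight.

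The steroid rules in protocol 5.7.2 sharpen this. Bursts may not take the total above 0.5 mg/kg, and no other increase is permitted. A subject who follows the protocol therefore cannot cross the line by a dose increase. Such a subject can meet the item only through the background dose brought into the study, or through weight loss on a fixed dose. Neither is a flare.

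At stake are severe-flare incidence, overall flare incidence (unless the same subject has another flare) and severe time to flare. The SAP has no programmed check that would remove a literal entry made by a site.

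**Working it through.** **Inputs.** The threshold is 0.5 mg/kg/day (SAP 15.3.8; protocol 6.2.2). The highest stable entry dose is 40 mg/day (criterion 9a). Each planned group has 8 subjects, with 32 active subjects in total (protocol 4.1). The documents give no distribution of entry weight or steroid dose, so the weights below are assumptions shown over a range. The plan states no figure of its own on this point to reproduce.

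**Who meets the item at entry.** Dose per kg = D / weight. The item is met when D / weight > 0.5, that is, when weight < 2D kg.

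| Stable dose | Met below | Examples (mg/kg/day) |
|---|---|---|
| 40 mg/day | 80 kg | 50 kg: 0.80; 60 kg: 0.67; 70 kg: 0.57; 79 kg: 0.51; 80 kg: 0.50 (not met) |
| 30 mg/day | 60 kg | 50 kg: 0.60; 60 kg: 0.50 (not met) |
| 20 mg/day | 40 kg | 60 kg: 0.33 (not met) |

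**Weight change alone.** At 40 mg/day, 80.5 kg gives 40/80.5 = 0.497 and 79 kg gives 40/79 = 0.506. A loss of 1.5/80.5 = 1.9% crosses the line on a constant dose.

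**When a literal entry would be dated.** SAP 15.1 uses the visit date if no event date is recorded. The first visit for flare incidence in protocol 6.2.3.3 is Day 22, which is 22 − 1 = 21 days after randomization.

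**Effect of one false event, with no other severe flare in the group.**

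- Incidence with 8 evaluable: 0/8 (Wilson 95% CI 0 to 32.4%) becomes 1/8 = 12.5% (2.2 to 47.1%).
- Incidence with 7 evaluable: 1/7 = 14.3% (2.6 to 51.3%).
- Kaplan-Meier just after the event, with no earlier event or censoring: 7/8 = 0.875 in one group. If the subject is on active drug, 31/32 = 0.969 for all active subjects combined.
- Fisher's exact test, two-sided, 1/8 versus 0/8: with one event in 16 subjects, each of the two possible tables has probability 0.5, so p = 1.00.

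Starting from zero events, one such entry changes the description but not the test.

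**The case against.** The strongest reply is that harm needs an unlikely reading. Sites judge flares; they are not programmed from dose data. The surrounding text speaks of incidence and of time to a first event, so an investigator would have to record a severe lupus flare in a patient whose disease and treatment had not changed. The protocol also refers details of its scales to a study reference manual, and eCRF instructions may exist; neither was available for this review. These points stand and lower the likely effect. They do not remove the defect, because no text in either document excludes a subject already above the line. With about 20 sites for about 40 subjects, uniform recording depends on the written definition.

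A reader might infer that the item biases the comparison with placebo. The documents do not support that. The background dose is set before double-blind randomization within each cohort, so literal entries should be unrelated to treatment apart from chance imbalance.

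A reader might also infer that permitted bursts count as severe flares. They do not: the burst cap is 0.5 mg/kg in total, and the item requires more than that.

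Finally, a reader might infer that treatment failure is contaminated. Protocol 6.2.3.3 does list a possible failure outcome that includes SLE flare, but SAP 15.3.13 does not use it.

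**Conclusion.** The point holds as a minor one. As written, the item classes an eligible subject on an unchanged dose as having a severe flare; at 40 mg/day this applies at any weight under 80 kg. That is a stated rule giving a wrong answer, not merely missing detail.

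The practical effect is conditional and small. It requires at least one subject enrolled above 0.5 mg/kg/day, or drifting above it through weight loss, and a site that records the item literally. Neither can be counted from the documents, and the number affected may be zero. The outcomes concerned rank low even among the exploratory ones. Day 85 SRI, the safety analyses and the SAP's treatment-failure definition do not use this item. The case for acting is that the definition is easily corrected, not that a large distortion is expected.

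**What to change.** In protocol 6.2.2 and SAP 15.3.8, replace the item with: *increase in prednisone (or equivalent), after randomization, to a total > 0.5 mg/kg/day*. Carry the same wording into the eCRF and site guidance, since sites make the entry and a SAP edit alone would not change the data. The guidance should say that a change in weight alone, or resuming a prescribed dose after a missed one, is not an increase.

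Check at 60 kg:

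- Stable 40 mg (0.67): not a flare.
- 10 mg with a permitted burst to 30 mg (0.50): item not met.
- 40 to 50 mg (0.83): counts. Protocol 5.7.2 does not permit this increase, so it would be rescue or a deviation.
- Permitted taper from 40 to 20 mg (0.33), then back to 40 mg (0.67): counts, although the total never exceeds the entry dose.

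One limit remains. A small re-escalation wholly above the line, such as 35 to 40 mg at 60 kg (0.58 to 0.67), still counts as severe, as it does now.

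The cost is a short text change at the next protocol amendment, with the ethics review that entails, a matching SAP edit and a notice to sites. No new data, visits or analyses are needed: weight is already measured at every flare-assessment visit, and protocol 5.7 already requires medication changes to be reported. The burst rules in 5.7.2 stay as they are.
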